3.1.1 Formulation

The drug product is bomedemstat, a bis-tosylate salt. The free base of bomedemstat is the active moiety. Bomedemstat will be supplied in capsules of multiple strengths. These strengths, based on bomedemstat free base, i.e. the active substance, may include: 5 mg, 10 mg, 25 mg, and 50 mg. Additional strengths may be added over the duration of the study. Such details will be included via updates to the Pharmacy Manual. Details on capsules, including strengths, colors, and sizes, can be found in the pharmacy manual.

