3.1.4 Dosage

All patients will be treated daily until disease progression that meets criteria to discontinue treatment, or unacceptable toxicity (see Section 6.6). Dosing will begin on Day 1 at the starting dose (D_s), which is 0.5 mg/kg/d bomedemstat free base for all patients with a platelet count $\geq 100 \times 10^3/\text{mcL}$, and 0.4 mg/kg/d for patients with a platelet count of $75-99 \times 10^3/\text{mcL}$. The calculated dose will be rounded to the nearest 5 mg increment for dispensation and administration. Details on the selection of and rationale for the starting dose and dosing schedule can be found in Section 2.7.

Using dose titration, all patients will be dosed to the bomedemstat D_{pi} (platelet inhibitory dose), which reflects the on-target activity of the drug. The D_{pi} is anticipated to be $\leq 2 \text{ mg/kg/d}$; however, this is not the upper limit for titration purposes as the dose needed to achieve a therapeutic effect will vary among patients and may change over time. The platelet titration target expected to be associated with a clinically significant therapeutic effect is a platelet count of *approximately* $\geq 50 \times 10^3/\text{mcL}$ to $\leq 99 \times 10^3/\text{mcL}$. Titration and re-challenge rules based on evaluation of platelet, ANC, and Hgb counts are described in Section 6.2. The maximum dose is 6 mg/kg/d.

Bomedemstat dosing will be based on the patient's weight on the first day of study treatment. If during the study the patient's weight differs from Day 1 by more than 10%, the amount of bomedemstat dispensed should be updated to the current weight. The source data must clearly document the weight used.

In the event of uncertainty regarding dose modification of bomedemstat for adverse events, or uncertainty regarding management of clinically significant changes in platelets, neutrophil counts, or other hematologic parameters, the PI should be consulted.

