6.0 TREATMENT PLAN

6.1 Study Overview

This is an open label, single arm, single institution Phase 1-2 study testing the activity and tolerability of the LSD1 inhibitor bomedemstat in combination with maintenance immune checkpoint inhibitor (ICI) in patients with newly diagnosed extensive stage SCLC treated with first-line induction platinum-etoposide and ICI. Bomedemstat dosing will be titrated to platelet count suppression (an on-target toxicity). Consideration of bomedemstat dose escalation will occur on an every three week schedule. As such, for convenience, all patients will receive the ICI atezolizumab in combination with bomedemstat, including patients who received a different ICI as part of induction with platinum-etoposide.

The starting dose of bomedemstat will be determined according to the screening platelet count as follows. For patients with a platelet count of $\geq 100 \times 10^3/\text{mCL}$, the starting dose will be 0.5 mg/kg/d. For patients with a platelet count of $75-99 \times 10^3/\text{mCL}$, the starting dose will be 0.4 mg/kg/d. See Sections 2.7 and 3.1.4 for bomedemstat starting dose selection rationale. A safety evaluation will be performed as described in Section 10.2 and the starting dose will be modified accordingly, if necessary.

Bomedemstat will be administered orally, once daily, for a 21-day cycle. Bomedemstat should be taken on an empty stomach. See Section 3.1.5 for detailed administration instructions. Because bomedemstat exhibits on-target toxicity of lineage-specific myelosuppression that preferentially affects platelet production, bomedemstat dosing will be titrated to a target platelet count of $50-99 \times 10^3/\text{mCL}$ as described in Section 6.2. Detailed guidance regarding bomedemstat dose modification for toxicities (including myelosuppression) is described in Section 6.3.

Atezolizumab will be administered via IV infusion at a flat dose of 1,200 mg every 3 weeks in keeping with the medication's prescribing information regarding standard of care use⁴⁶.

Subjects who at any time experience severe toxicity meeting criteria for treatment discontinuation (see Section 6.6.2) will not be eligible for further study treatment and will be converted to Off Treatment status.

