6.2 Bomedemstat Dose Titration to Platelet Count

Bomedemstat dose titration to platelet count will be performed according to the titration and re-challenge rules described in Table 6.1 and Table 6.2 as follows. Dose titration rules use the absolute platelet count and the relative change from the most recent scheduled assessment. Prior to cycle 2 day 1, dose increases are not permitted, and dose titration should be performed according to Table 6.1. Starting on Day 1 of cycle 2, dose increases are permitted, and dose titration should be performed according to Table 6.2. The maximum allowed dose is 6 mg/kg/d. Dose increases require adequate neutrophil and erythrocyte indices, and dose increases are not permitted within 21 days of a previous dose change, where change is inclusive of dose increase or dose reduction. After a dose hold, when platelets have returned to $>50 \times 10^3/\text{mCL}$, the subject should be re-challenged with bomedemstat at 50% of the previous dose. Dose reductions for safety reasons are permitted at any time.

Table 6.1. Bomedemstat titration to goal platelet count and re-challenge rules for cycle 1, days 8 and 15.

Platelet Assessment		Rules		
Platelet count ($\times 10^3/\text{mCL}$)	Change in Platelet Count Relative to Previous Scheduled Assessment	Titrate Dose?	Titration Rule	Re-challenge Rule
≥ 100	Any, including same count	Maintain	N/A	N/A
50-99	Any increase or same count	Maintain	N/A	N/A

50-99	<50% decrease ¹	Down-titrate ¹	Decrease current dose by 0.1 mg/kg¹	N/A
50-99	≥50% decrease ¹	Down-titrate ¹	Decrease current dose by 0.2 mg/kg if starting dose was 0.5 mg/kg or by 0.1 mg/kg if starting dose was 0.4 mg/kg¹	N/A
<50	Any change ¹	HOLD DOSE¹	HOLD DOSE¹	Resume at 50% of previous dose when platelets return to $>50 \times 10^3/\text{mCL}$. ²

1. If pseudothrombocytopenia due to blood sample coagulation or platelet clumping is suspected, the CBC should be repeated. If the second blood draw confirms that the first draw yielded a falsely low platelet count, the result of the first draw should be ignored and the dose of bomedemstat calculated based on the result of the second draw.
2. ANC $\geq 1.0 \times 10^3/\text{mCL}$ ($1.0 \times 10^9/\text{L}$) and Hgb $\geq 8 \text{ g/dL}$ (80 g/L) are needed for or re-challenge.

Table 6.2. Bomedemstat titration to goal platelet count and re-challenge rules for all days with CBC evaluation in cycle 2 and beyond.

Platelet Assessment		Rules		

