Platelet count (x 10 ³ /mCL)	Change in Platelet Count Relative to Previous Scheduled Assessment	Titrate Dose?	Titration Rule	Re-challenge Rule
≥200	Any, including same count	Up-titrate ^{1,2,3}	Increase current dose by 0.15 mg/kg	N/A
100-199	<75% decrease ⁴ or same count or any increase	Up-titrate ^{1,2,3}	Increase current dose by 0.1 mg/kg	N/A
100-199	≥75% decrease ⁴	Maintain ⁴	N/A	N/A
50-99	<50% decrease ⁴ or same count or any increase	Maintain ⁴	N/A	N/A
50-99	≥50% decrease ⁴	Down-titrate ⁴	Decrease current dose by 0.1 mg/kg or 25% , whichever results in a lower dose	N/A
<50	Any change ⁴	HOLD DOSE⁴	HOLD DOSE⁵	Resume at 50% of previous dose when platelets return to > 50x10 ³ /mCL. ¹

1. ANC ≥ 1.0 x 10³/mCL (1.0 x 10⁹/L) and Hgb ≥ 8 g/dL (80 g/L) are needed for up-titration or re-challenge.
2. Dose up-titration is not permitted if any dose change (including up- or down-titration) has occurred within the previous 21 days.
3. The maximum allowed dose of bomedemstat is 6 mg/kg/d.
4. If pseudothrombocytopenia due to blood sample coagulation or platelet clumping is suspected, the CBC should be repeated. If the second blood draw confirms that the first draw yielded a falsely low platelet count, the result of the first draw should be ignored and the dose of bomedemstat calculated based on the result of the second draw.
5. Prophylactic platelet transfusion is at the discretion of the treating investigator. Prophylactic platelet transfusion is strongly encouraged for platelet count < 10x10³/mCL.

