10.2 Safety Evaluation

The DLT assessment period is 21 days from initiation of treatment. The first 6 eligible patients who receive at least one dose of bomedemstat and atezolizumab with at least 21 days of follow-up (safety analysis population) will be closely monitored for toxicities. If more than 2 patients experience DLTs (see Section 9.5), then the starting dose of bomedemstat for a given platelet count will be reduced by 0.1 mg. Otherwise, accrual will proceed as described in Section 10.3. If the dose is reduced, following 6 additional patients meeting the criteria to be assessed for DLTs, the same rules will apply (continue at dose if <3 patients with DLT and dose reduce by 0.1 mg if >2 with DLT).

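### The DLT-triggered cut in the bomedemstat starting dose is written as 0.1 mg, very probably for 0.1 mg/kg/d, and read literally it changes almost nothing

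*Combined protocol and SAP*

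**What the plan says.** Section 10.2 (Safety Evaluation) follows the first 6 eligible treated patients for 21 days. If more than 2 have a DLT, "then the starting dose of bomedemstat for a given platelet count will be reduced by 0.1 mg". The same rule then applies to 6 more patients at the reduced dose, and the amount is restated: "dose reduce by 0.1 mg if >2 with DLT". Neither statement has a per-kilogram or per-day unit.

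The quantity being reduced is defined only per kilogram. Sections 2.7, 3.1.4 and 6.1 set it at 0.5 mg/kg/d for platelets of 100 x 10^3/mcL or more. For platelets of 75-99 x 10^3/mcL, Section 6.1 says "the starting dose will be 0.4 mg/kg/d".

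Section 3.1.4 adds: "The calculated dose will be rounded to the nearest 5 mg increment for dispensation and administration". The capsule strengths in Section 3.1.1 "may include: 5 mg, 10 mg, 25 mg, and 50 mg", so 5 mg is the smallest listed, although further strengths may be added.

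Section 6.1 leaves the cohort-level change to Section 10.2: "A safety evaluation will be performed as described in Section 10.2 and the starting dose will be modified accordingly, if necessary". No other section gives the size or unit of this step.

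**The concern.** The step and the dose it modifies are in different units. An absolute 0.1 mg is one-fiftieth of the 5 mg rounding increment, so a literal reading makes the reduction almost empty.

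This is the only rule that sets a new starting dose for the cohort after a failed safety run-in, and safety and tolerability is one of the two primary objectives in Section 1.1. Followed exactly, it would start most of the next 6 patients on the dispensed dose that had just exceeded the DLT limit. If staff instead supply the missing unit, the dose tested in the second group of 6 rests on their inference and not on the protocol.

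**Working it through.** The 0.1 mg step is a stated constant, so there is no derivation in the plan to reproduce. The check is what the step does to the dispensed dose under each reading.

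**Inputs.** Starting doses of 0.5 and 0.4 mg/kg/d (Sections 3.1.4 and 6.1); rounding to the nearest 5 mg (Section 3.1.4); step of 0.1 mg (Section 10.2). Body weight is not in the documents; 40 to 120 kg is assumed, with every weight on the grid counted equally. The plan does not say how ties round, so ties up, down and to even were all tried.

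**Formulas.** Calculated dose = starting dose x weight. Literal reading: subtract 0.1 mg, then round. Per-kilogram reading: subtract 0.1 mg/kg x weight, then round.

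**Example at 70 kg.**

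| Starting dose | Calculated, dispensed | After 0.1 mg | After 0.1 mg/kg/d |
|---|---|---|---|
| 0.5 mg/kg/d | 35 mg, 35 mg | 34.9 mg, dispensed 35 mg (0.1/35 = 0.3% cut) | 28 mg, dispensed 30 mg (7/35 = 20% cut) |
| 0.4 mg/kg/d | 28 mg, 30 mg | 27.9 mg, dispensed 30 mg (0.1/28 = 0.4% cut) | 21 mg, dispensed 20 mg (7/28 = 25% cut) |

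The percentages are cuts in the calculated dose.

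**Literal reading, weights to 0.1 kg (801 weights).** The dispensed dose changes at 16 weights at 0.5 mg/kg/d (2.0%) and at 14 to 21 weights at 0.4 mg/kg/d (1.7% to 2.6%), depending on ties. It is therefore unchanged at 97.4% to 98.3% of weights. Where it does change, the calculated dose sat at or just above a rounding boundary, and the patient drops a full 5 mg by accident of weight.

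**Literal reading, whole-kilogram weights (81 weights).** Changes occur at 0 to 8 weights at 0.5 mg/kg/d and 0 to 4 at 0.4 mg/kg/d, so the dose is unchanged at 90.1% to 100%. The low end, (81 - 8)/81 = 90.1%, is 0.5 mg/kg/d with ties rounded up.

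**Per-kilogram reading, weights to 0.1 kg.** The dispensed dose changes at 788 or 789 of 801 weights at 0.5 mg/kg/d (98.4% to 98.5%) and at 780 of 801 at 0.4 mg/kg/d (97.4%). The exceptions lie only at 43.8 to 45.0 kg and 41.7 to 43.7 kg respectively.

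**Which unit was meant.** Every other fixed-amount bomedemstat step is weight-based. Table 6.1 has "Decrease current dose by 0.1 mg/kg" (and 0.2 mg/kg in one row), Table 6.2 uses 0.1 and 0.15 mg/kg, and Tables 6.3 and 6.4 reduce by 0.1 mg/kg/d. The two starting doses differ by 0.5 - 0.4 = 0.1 mg/kg/d.

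**How often the rule would operate.** With X the number of DLTs among 6 patients and true rate p, P(X >= 3) = 1 - [P(0) + P(1) + P(2)]:

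- p = 20%: 1 - (0.262 + 0.393 + 0.246) = 0.099
- p = 30%: 1 - (0.118 + 0.303 + 0.324) = 0.256
- p = 40%: 1 - (0.047 + 0.187 + 0.311) = 0.456

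These DLT rates are assumptions; the plan gives none.

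**The case against.** The strongest reply is that this is a typographical slip with only one workable reading. The starting dose is defined in mg/kg/d throughout, and subtracting 0.1 mg from about 35 mg when the smallest listed capsule is 5 mg is visibly unworkable and would prompt a query. Section 3.1.4 sends uncertainty about dose modification for adverse events to the PI. The trial is at one institution, with weekly review of data and adverse events by the PI and staff (Section 12.0) and review of adverse events and stopping rules by the data and safety monitoring committee (Section 11.1). Individual titration and holds (Sections 6.2 and 6.3) and the stopping rules in Sections 10.2.1 and 10.2.2 still apply. The pharmacy manual might also cover the step, but it is not among the documents.

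Much of this stands. Staff would probably read the step as 0.1 mg/kg/d, and patients would not be unprotected. The exact percentages depend on the assumed weights and tie rule, and mainly confirm that 0.1 mg is far below 5 mg.

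It does not remove the point. Titration acts after a patient has started, and the stopping rules end the study; neither sets the starting dose of the next 6 patients. The error appears in both statements of the rule, and nothing elsewhere in the protocol corrects it.

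**Conclusion.** The concern holds: the unit in Section 10.2 is wrong as written. That /kg/d was dropped is an inference, though a well-supported one.

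The literal rule leaves the dispensed starting dose unchanged at about 97% to 98% of weights, assuming 40 to 120 kg recorded to 0.1 kg. The per-kilogram reading cuts the calculated dose by 20% or 25% and changes the dispensed dose at about 97% to 98% of the same weights.

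This should be fixed because the rule is operative and bears on a primary safety objective. It does not affect the efficacy endpoint or the sample size.

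**What to change.** In Section 10.2, replace 0.1 mg with 0.1 mg/kg/d in both places, after the sponsor confirms that this is the intended amount. A first reduction would then give starting doses of 0.4 mg/kg/d (platelets 100 x 10^3/mcL or more) and 0.3 mg/kg/d (platelets 75-99 x 10^3/mcL); stating these two values in the text would remove any doubt.

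The first reduction survives the 5 mg rounding except at about 42 to 45 kg. A second reduction has a similar gap: at 40 kg in the lower-platelet group, 0.3 x 40 = 12 mg and 0.2 x 40 = 8 mg both round to 10 mg. The sponsor may wish to say that the dispensed dose must fall by at least 5 mg when a reduction is triggered.

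The cost is one wording amendment submitted to the IRB as a modification, with no extra patients, visits or analyses.

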6.3 Dose Modification for Toxicity

Toxicity will be graded using Common Terminology Criteria for Adverse Events (CTCAE version 5.03). Dose modification of bomedemstat for hematologic toxicities is listed in Table 6.3. Please note that use of hematopoietic growth factors is prohibited during study participation (see Section 6.4.3). Dose modification of bomedemstat for other toxicities potentially related to bomedemstat is listed in Table 6.4. If multiple toxicities suggesting conflicting dose modifications are present simultaneously, the rule that results in the lowest bomedemstat dose should be followed.

Dose modification, interruption, or discontinuation of atezolizumab for toxicity should be performed according to the prescribing information⁴⁶.

Subjects that require more than three down-titrations or dose holds of bomedemstat will render the subject ineligible for further treatment in the study and the subject will be converted to Off Treatment status.

Furthermore, encephalopathy of any grade is always considered a serious adverse event as well as an unacceptable toxicity and should result in immediate treatment discontinuation (see Sections 8.6.1 and 10.2.1).

Table 6.3. Dose modification of bomedemstat related to hematologic toxicities.

Toxicity	Grade	Management ¹
Neutropenia	3 (ANC 0.5-1x10 ³ /mcL)	Continue bomedemstat dosing and maintain dose level.
	4 (ANC <0.5x10 ³ /mcL)	Hold bomedemstat dosing until ANC recovery to $\geq 1.0 \times 10^3$ /mcL. Reduce dose by 0.1 mg/kg/d upon reinitiating.
Febrile Neutropenia	≥ 3	Hold bomedemstat dosing for at least 7 days and until ANC recovery to $\geq 1.0 \times 10^3$ /mcL. Reduce dose by 0.1 mg/kg/d upon reinitiating.
Anemia	3 (Hgb <8 g/dL)	Continue bomedemstat dosing and maintain dose level. Transfusion of red blood cells is at the discretion of the treating physician and does not require bomedemstat dose modification.
	4 (Life-threatening consequences; urgent intervention indicated)	Hold bomedemstat dosing until Hgb recovery to ≥ 8 g/dL. Reduce dose by 0.1 mg/kg/d upon reinitiating.
Thrombocytopenia	See Table 6.1 and Table 6.2.	
Lymphopenia	Any	Dose interruption or study discontinuation is not required for lymphopenia of any grade.

1. Use of hematopoietic growth factors is prohibited during study participation (see Section 6.4.3).

Table 6.4. Dose modification of bomedemstat related to non-hematologic toxicities.

Type	Grade	Management			

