		Hold treatment?	Timing for restarting treatment	Dose/schedule for restarting/treatment	Discontinue subject? (After consultation with PI)
Non-laboratory	1	No	N/A	N/A	N/A
	2	Consider withholding for persistent symptoms	Toxicity resolves to Grade 0-1 or baseline	Reduce dose by 0.1 mg/kg/d upon reinitiating.	Toxicity does not resolve to Grade ≤ 1 or baseline

	3, lasting >3 days despite optimal supportive care	Yes			within 4 weeks of last dose. Permanent discontinuation should be considered for any severe or life-threatening event.
	4	Yes			
Laboratory, non-hematologic or hematologic not listed in Table 7-4	1-2	Consider withholding for clinically significant abnormalities following consultation with study PI	N/A	N/A	N/A
	3-4, if medical intervention is required or abnormality leads to hospitalization	Yes	Toxicity resolves to Grade 0-1 or baseline	Reduce dose by 0.1 mg/kg/d upon reinitiating.	Toxicity does not resolve to Grade ≤1 within 4 weeks of last dose. Permanent discontinuation should be considered for any severe or life-threatening event.

In case clinically significant non-hematologic toxicity does not resolve to Grade 0-1 or baseline within 4 weeks after last dose of any study treatment, investigational treatment with bomedemstat should be permanently discontinued, and the subject should be converted to Off Treatment status. Clinical significance is at the discretion of the investigator. With investigator and sponsor agreement, subjects with a non-hematologic laboratory adverse event still at Grade 2 after 4 weeks may continue treatment in the study and retain On Treatment status only if asymptomatic and controlled.

Subjects who experience a recurrence of the same severe or life-threatening event at the same grade or greater following re-challenge of bomedemstat are not eligible for further study treatment and should be converted to Off Treatment status.

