10.2.1 Stopping Rule for Encephalopathy

Due to the previous association of LSD1 inhibitors with encephalopathy²⁸, the occurrence of encephalopathy of any grade at any point during study participation will result in immediate study discontinuation and cessation of study treatment for all subjects.

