10.2.2 Stopping Rule for Recurrent Toxicity

If four or more patients experience unacceptable toxicity requiring permanent cessation of study treatment, the study will be immediately discontinued, and study treatment will cease for all subjects.

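### A failed reduced-dose DLT cohort leads only to another bomedemstat reduction; in the protocol text the DLT count triggers no study-level stop and no required independent review

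*Combined protocol and SAP*

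**What the plan says.** Section 10.2 follows the first six evaluable patients for 21 days. If more than two have a DLT, the starting dose for each platelet stratum is lowered by one step, printed as 0.1 mg and read here as 0.1 mg/kg/d. If not, "Otherwise, accrual will proceed as described in Section 10.3". After a reduction, six more patients are assessed under the same rule: "continue at dose if <3 patients with DLT and dose reduce by 0.1 mg if >2 with DLT".

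Section 9.5 counts toxicities related to either bomedemstat or atezolizumab as DLTs. They include febrile neutropenia, thrombocytopenia with serious bleeding or a need for prophylactic transfusion, prolonged grade 3 and any grade 4 non-hematologic toxicity, certain laboratory events, and grade 5 toxicity.

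Two rules stop the whole study:

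- Section 10.2.1: "the occurrence of encephalopathy of any grade at any point during study participation will result in immediate study discontinuation".
- Section 10.2.2: "If four or more patients experience unacceptable toxicity requiring permanent cessation of study treatment", the study ends at once. This rule has no time limit.

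Section 8.6.1 requires SAEs to be reported within 24 hours. Section 12.0 provides weekly review by the principal investigator and research staff. Section 11.1 provides independent monitoring visits, DSMC review as needed, and IRB review of risk and benefit, under an institutional monitoring plan that is not in the file.

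**The concern.** A first failed cohort suggests that the starting dose is too high, and lowering it is a sensible reply. A second failure at the lower dose raises a different question: whether bomedemstat dose is the problem at all. Toxicity from atezolizumab, or from the combination, may not yield to less bomedemstat. Section 2.5 says that adding LSD1 inhibition to checkpoint inhibition had not yet been tested in clinical trials.

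At that point the written rule still prescribes another reduction and a further cohort. Whether anyone outside the study team considers the data before the next patient starts depends on general oversight, not on a trigger in 10.2. Safety is a primary objective, so this decision deserves a stated rule.

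**Working it through.** **1. Do the existing stops respond to DLTs?** Section 10.2.1 responds to encephalopathy only. Section 10.2.2 responds to permanent cessation, so the DLTs in 9.5 must be compared with how the protocol manages them.

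- Febrile neutropenia (Table 6.3): "Hold bomedemstat dosing for at least 7 days and until ANC recovery to" the stated threshold, then restart 0.1 mg/kg/d lower.
- Platelets below 50 x 10³/mcL (Tables 6.1 and 6.2): hold, then resume at 50% of the previous dose.
- Non-hematologic grade 3 lasting over 3 days, or grade 4 (Table 6.4): hold, then restart lower on resolution. The table adds: "Permanent discontinuation should be considered for any severe or life-threatening event".
- Events that do end treatment: grade 5 toxicity, encephalopathy, grade 3 or higher infusion reaction (6.6.2), clinically significant non-hematologic toxicity unresolved at 4 weeks, recurrence of the same severe event on re-challenge, and the limit on repeated modifications: "Subjects that require more than three down-titrations or dose holds of bomedemstat".
- Atezolizumab: "Dose modification, interruption, or discontinuation of atezolizumab for toxicity should be performed according to the prescribing information". That label is not in the file.

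The share of DLTs that count toward 10.2.2 is therefore unknown. Two failed cohorts mean at least 3 + 3 = 6 patients with DLTs, and these need not produce four cessations.

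**2. How likely is one failed cohort?** The protocol gives no operating characteristics for the DLT rule, so there is no figure to reproduce. With X ~ Bin(6, p), a cohort fails if X ≥ 3. At p = 0.4:

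1 − (0.6⁶ + 6 × 0.4 × 0.6⁵ + 15 × 0.4² × 0.6⁴) = 1 − (0.047 + 0.187 + 0.311) = 0.456.

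| DLT rate p (assumed) | 20% | 30% | 40% | 50% | 60% |
|---|---|---|---|---|---|
| One cohort fails | 0.099 | 0.256 | 0.456 | 0.656 | 0.821 |
| Two in a row, same rate (square) | 0.010 | 0.065 | 0.208 | 0.431 | 0.674 |

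**3. How likely are two failures without a 10.2.2 stop?** Let c be the share of DLT patients who stop permanently for toxicity, and d the same share among patients without a DLT. Both are assumed. Cessations per cohort are Bin(X, c) + Bin(6 − X, d). The table gives the probability that both cohorts fail and that total cessations are below four.

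| c | d | p = 20% | 30% | 40% | 50% | 60% |
|---|---|---|---|---|---|---|
| 25% | 0 | 0.9% | 6.1% | 19% | 39% | 59% |
| 50% | 0 | 0.6% | 3.7% | 11% | 20% | 26% |
| 75% | 0 | 0.1% | 0.8% | 2% | 3% | 3% |
| 25% | 20% | 0.7% | 4.7% | 15% | 30% | 47% |
| 50% | 20% | 0.3% | 1.9% | 6% | 11% | 15% |
| 75% | 20% | 0.05% | 0.3% | 0.7% | 1.2% | 1.3% |

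**4. What if the reduction helps?** Suppose the DLT rate falls 10 points in the second cohort (40 to 30%, 50 to 40%, 60 to 50%). With d = 20% the results are 8/21/38% at c = 25%, 3/8/13% at c = 50% and 0.5/0.9/1.3% at c = 75%. With d = 0 they are 11/27/48%, 6/14/22% and 1.2/2.5/3.1%.

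Encephalopathy stops are not modelled and would lower every figure.

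**5. Accrual.** Section 10.4 expects 34 patients in 24 months: 34/24 = 1.4 per month. Two cohorts of six take about 12/1.4167 = 8.5 months.

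**The case against.** The best defence is that the protocol is well supervised and that the troubling scenario is unlikely. Most of this stands.

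- Many DLTs would also be SAEs, reported to the principal investigator within 24 hours, and those needing expedited reporting also go to the IRB and FDA. Section 11.1 has committees evaluate accrual, adverse events and stopping rules, and makes committee approval, as applicable, necessary to continue. Six or more DLTs over some 8.5 months would be unlikely to pass unseen.
- Grade 5 DLTs, investigator judgement under 6.6.2 and the advice in Table 6.4 to consider discontinuation all push the cessation share upward, toward the low rows of the table. Because 10.2.2 has no time limit, early patients keep contributing to it.
- No DLT rate of 40% or more has support in the documents. Section 2.7 describes myelosuppression as dose-dependent and reversible. It reports no DLTs in two studies whose selected starting dose, 0.6 mg/kg/d, was higher, though these were in other diseases.

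A reader might infer that the trial has no toxicity stopping rule, or that nobody independent would look. The documents support neither: 10.2.1 and 10.2.2 can end the study, and 11.1 provides independent oversight. The institutional plan may even contain a toxicity trigger. The gap is established for the protocol text only.

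A reader might also make much of the missing lowest dose and the missing explicit accrual hold. Both are minor. Taking the 0.4 mg/kg/d stratum to zero needs four steps of 0.1, hence four failed cohorts in a row (at least 12 DLT patients) with fewer than four cessations, and 34 patients allow at most five full cohorts. On accrual, the text already makes proceeding conditional on passing, and about one patient (1.4 × 21/30.4) would enrol during a 21-day window.

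What the defence does not supply is a written response, other than reduction, to a second failed cohort.

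**Conclusion.** The point holds as a cheap improvement, not as a serious defect. For a cohort that fails at an already reduced dose, 10.2 states one response, and that response may not address toxicity from atezolizumab or the combination. The protocol attaches no study-level stop or required independent review to the DLT count, and the 10.2.2 limit need not be reached.

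At DLT rates of 20-30% the chance of two failed cohorts without a 10.2.2 stop is about 6% or less in every row. At 40-60% it is 6-59% if half or fewer of DLTs end treatment and the rate stays constant, or 3-48% if the rate falls 10 points after the reduction. It is about 3% or less if three quarters of DLTs end treatment. These figures rest on assumed DLT rates, assumed cessation shares and independence between patients, and the documents give none of these. They describe when the gap would matter, not how likely it is in this trial.

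**What to change.** Add to 10.2: if more than 2 of 6 patients have DLTs in a cohort treated after a starting-dose reduction, accrual is suspended and the data go to the Consortium DSMC. Before any further enrolment, the committee decides whether to stop, to reduce further (and to what lowest dose), or to continue.

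This takes one sentence and uses a committee already named in 11.1. Leaving the lowest dose to that decision also settles the missing floor. The cost arises only if a second cohort fails: an accrual pause that delays about 1.4 patients per month.
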